### **3.2 Number of Patients**

The study team will enroll eight patients in the study.

### **3.3 Study Duration**

Based upon the duration of funding and a conservative estimate of accrual the duration of the clinical trial will be approximately one year.

### **3.4 Study Completion**

The study will reach completion after the last evaluable patient completes protocol therapy.

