## STUDY SCHEMA

## STUDY CALENDAR

Period/Procedure	Screening	ATB Administration: (Daily till Day -1 of Surgery)			End of ATB administration
		Study Day/Visit Day	-14 to 0 Days 	Day 1	Midway during ATB administration
Informed Consent	X				
Physical Examination 	X				X
Medical History 	X				
Vitals			X		
Concomitant Medications	X		X		X
ATB Administration			X		X
Pregnancy Test (Serum or Urine) 	X				
ECOG Performance Status 	X				X
AE Assessment	X		X		X
Complete Blood Count (CBC) With Differential and Platelet Count	X				X
PT, INR					X
Complete Metabolic Panel 	X			X 	X
Research Blood 			X		
Research Saliva Samples 		See footnote 8 for research saliva sample draw timepoints			
Tumor Specimen 	X				X
Patient Diary 			X		X
Compliance Assessment 					X

1. Screening procedures must occur within 14 days prior to registration. ATB administration should start within seven days of registration.
2. Focused physical examination
3. Capture medications taken within 14 days of day 1 of ATB administration
4. For women of childbearing potential.
5. Refer to Appendix 1.
6. Including albumin, total protein, total bilirubin, direct bilirubin, ALT, AST, LDH, alkaline phosphatase, bicarbonate, sodium, potassium, chloride, creatinine, magnesium, calcium, BUN, and glucose.
7. Day 1: Blood samples will be taken at baseline (prior to study agent administration), then at 30, 60, 120, 180, 240, 360, 480, and 1,440 min (a total of nine points). For each blood draw 1 ml of blood will be drawn to yield approximately 500  $\mu$ l or 0.5 ml of plasma. All blood sample collections are allowed a window of  $\pm$  10 minutes. **There will only be ONE ATB dose on day 1. Dose on day 2 must be delayed until completion of PK specimen (blood and saliva) collection.**
8. Day 1: Saliva samples (1 ml) should be collected at baseline (prior to study agent administration), then at 30, 60, 120, 180, 240, 360, 480, and 1,440 min (a total of nine points). Note: 30 min time point has  $\pm$  5 min window, all other time points have  $\pm$  10 min window. There will only be ONE ATB dose on day 1. All saliva sample collections are allowed a window of  $\pm$  10 minutes. Day 2 to day -1 of surgery: A total of at least three patient samples (saliva) will be collected for each time point (predose, before lunch, and before dinner).
9. Refer to Section 5.1.

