10. Patient will complete study diary (Appendix 2) with all relevant information and will submit the diary to study coordinator.
11. Study coordinator will contact patients twice weekly for compliance assessment and reminders for protocol procedures.
12. Chemistry panel with AST, ALT, T. Bilirubin will be performed approximately midway during treatment.
13. The indicated assessment for this timepoint will be collected only once with a window of 2 days: Day -2 to Day -1 of surgery.

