#### **4.9 End of Study Definition**

A participant is considered to have completed the study if he or she completed all phases of the study, including the last visit or the last scheduled procedure shown in the calendar of events or has been discontinued.

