## 6.2 Collection and Reporting Requirements for Adverse Events and Serious Adverse Events

### 6.2.1 Collection of Adverse Events

All (or specify if only certain grade AE needed) adverse events (including SAEs) must be recorded in OnCore® and/or an adverse event log. All AEs required to be collected must be graded according to the CTCAE v5. When possible, signs and symptoms indicating a common underlying pathology should be noted as one comprehensive event. Investigator's or treating physician's assessment of AE attributions must also be documented.

AEs will be collected from the time the subject signs the consent form through 30 days post last dose of study drug(s). AEs will be tracked and followed until resolution, subject withdraws consent, or is lost to follow-up (including subjects who discontinue early). All adverse events collected per the protocol will be followed with appropriate medical management until they are resolved, if they are related to the study treatment, or until the investigator deems the event to be chronic.

Please see section 6.2.2 and table 4 to identify the adverse events that need to be reported.

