### **7.2 Study Objectives and End Points**

The endpoint of the study is the successful evaluation of a PK profile, with estimation of PK parameters such as plasma and saliva AUC and Cmax. The study shall be deemed complete when the 6th evaluable patient has completed therapy and the samples sent for PK analysis.

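### AE collection is required for 30 days after the last dose, but no AE assessment is scheduled in that period and the completion rules can be met before it ends

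*Combined protocol and SAP*

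**What the plan says.** Two sets of rules bear on the end of follow-up.

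**Safety window.** Section 6.2.1: "AEs will be collected from the time the subject signs the consent form through 30 days post last dose of study drug(s". Section 6.2.2 gives SAE reporting the same end. Section 4.1 has a follow-up status that starts on the last treatment day, but gives the period no length, visit or contact.

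**Completion.**
- Section 3.4: "The study will reach completion after the last evaluable patient completes protocol therapy".
- Section 4.9, for the individual participant, refers to completing all phases, "including the last visit or the last scheduled procedure shown in the calendar of events".
- Section 7.2: "The study shall be deemed complete when the 6th evaluable patient has completed therapy and the samples sent for PK analysis".

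**Schedule.** The calendar has ATB taken daily up to the day before surgery. Its last column is the end of ATB administration, and that column holds the last AE assessment. Footnote 13 describes a timepoint "collected only once with a window of 2 days: Day -2 to Day -1 of surgery". There is no post-operative or 30-day column.

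**The concern.** A coordinator who follows the calendar and the completion rules to the letter has no planned occasion to ask about events after the operation, although section 6.2 says those events must be collected. The two parts of the protocol need to agree.

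This matters more here than in most PK studies because dosing runs up to the eve of surgery. The toxicity part of section 1.1 acknowledges that earlier trials did not specifically look at surgical risk, and it adds a pre-operative coagulation test as a safeguard. Bleeding and healing outcomes can only show themselves after that test and after the last scheduled AE assessment.

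A decision rule is also touched. Section 6.5 counts a DLT only if it occurs during the study, and it triggers the early safety assessment when the first four patients have completed therapy. That assessment can therefore take place before those patients' 30-day windows close. For the last patient, the completion wording leaves it unclear whether a late event still falls within the study.

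**Working it through.** The plan gives no figure to reproduce on this point. The check is a day count and a comparison of sections.

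**Inputs**
- Course length: 7 to 28 days (sections 2.1 and 5.1).
- Last dose: day -1, taking surgery as day 0 (calendar header).
- Last scheduled AE assessment: day -2 or day -1 (footnote 13, read as applying to the last column).
- Diary with symptom column handed in: day 0 (Appendix 2).
- AE and SAE window: 30 days after the last dose (6.2.1, 6.2.2).

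**Days with no scheduled AE assessment**
- End of window: -1 + 30 = day 29.
- From an assessment on day -2: 29 - (-2) = 31 days.
- From an assessment on day -1: 29 - (-1) = 30 days.
- If the diary hand-in counts as a contact: 29 - 0 = 29 days.

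**Share of the span from first dose to window end**
- 7-day course: 30 / (7 + 30) = 30/37 = 81%.
- 28-day course: 30 / (28 + 30) = 30/58 = 52%.

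The AE window in 6.2.1 opens at consent. Counting the days before the first dose as well would lower both shares.

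**Can each completion rule be met before day 29?**
- 3.4: yes. Therapy ends on day -1.
- 4.9: yes. The last calendar items fall just before surgery or, for the resected tumor, at surgery.
- 7.2: yes. The samples must also be sent, which probably puts completion after surgery, but no interval is given that would carry it to day 29. The rule also refers to the sixth evaluable patient, whereas section 3.2 enrolls eight, so other patients may have open windows too.

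**Does another procedure fill the gap?**
- The twice-weekly coordinator calls (footnote 11, Appendix 2) are for compliance and reminders. No continuation after ATB is stated.
- Section 10.4 has data entered on CRFs according to the calendar, which has no post-operative AE entry.
- Section 4.7 declares loss to follow-up only after failed contact at two consecutive calendar timepoints. With none after therapy, that rule cannot operate in the 30-day window, although 6.2.1 uses loss to follow-up as one end of AE tracking.
- The day-of-surgery items (specimens, diary, possibly the liver function test in section 3.1) are not post-operative AE assessments.

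**The case against.** The best defense is that the duty to collect events is intact. Section 6.2.1 has AEs tracked to resolution, 6.2.2 requires SAE reporting over the same 30 days, 4.6 keeps patients who stop treatment in follow-up with AEs still reported, and 4.1 moves a patient off study only when follow-up is complete. Section 3.4 does not say that AE collection stops. This stands: what is missing is a scheduled contact and consistent completion wording, not the obligation.

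Four stronger readings are tempting, and the documents do not support them.
- A reader might infer that post-operative events would surface only by chance. This is a single-site study, and prolonged hospitalization and medically important events count as SAEs (6.1.2). Routine surgical care and spontaneous reports may well reveal the serious ones. Lower-grade events after discharge are the more plausible gap.
- A reader might infer that post-operative event rates would be understated. No such rate is planned. The endpoints in 7.2 and 7.3 are PK parameters, and these are unaffected.
- A reader might infer that the study and its calendar end entirely before surgery. The resected tumor belongs to the last column, the diary and specimens come in on the day of surgery, and 7.2 waits for samples to be sent.
- A reader might take 52% to 81% as the fraction of events missed. It counts days only.

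It is also fair to say that the marker for footnote 13 is not visible in the table as read, so its placement is inferred. The gap does not depend on it, because no later column exists.

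**Conclusion.** The point holds as a conflict between stated rules. AEs and SAEs are required for 30 days after the last dose. No AE assessment is scheduled in that time, and sections 3.4, 4.9 and 7.2 can all be satisfied while it is running. About 29 to 30 days per patient, for up to eight patients, have nothing that actively elicits events, so post-operative AEs may not be captured systematically. The primary PK result is not at risk.

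The day count assumes that dosing continues to the day before surgery. A patient who stops ATB earlier has a window that closes earlier relative to the operation. The count also assumes that coordinator calls stop with ATB, since the documents state no continuation. Sections 3.4 and 7.2 also differ from each other and need reconciling in any case. The change is worth making because it schedules what section 6.2 already requires.

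**What to change.** 1. Add to the calendar one AE contact at about 30 days after the last dose, by telephone or at a routine post-operative visit, with a matching CRF entry.
2. State in section 4.1 that the follow-up period ends when that 30-day window closes, and let section 4.9 count a participant as complete only after it.
3. Reconcile 3.4 and 7.2 so that study completion follows the close of the last enrolled patient's 30-day window. The sixth-evaluable-patient condition can stay in 7.2 as the milestone for PK data.
4. Say in section 6.5 whether events in the 30 days after the last dose count as occurring during the study, and whether the four-patient assessment waits for them.

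The cost is at most eight short contacts and about one month at the end of the study. PK analysis need not wait, since the samples can be sent as now planned.

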## **4 SUBJECT PARTICIPATION, DISCONTINUATION AND WITHDRAWAL**

MCW personnel must follow all MCW IRB requirements and policies regarding subject participation, found here:

<https://www.mcw.edu/HRPP/Policies-Procedures.htm>

### **4.1 Subject Status**

**Subject statuses throughout the trial are defined as follows:**

- Prescreening: pre-consent (subject considering trial or study staff considering patient for the trial per institutional recruitment methods).
- Screening: period after consent, but prior to eligibility confirmation.
- Consented: consented, prior to eligibility confirmation.
- Eligible: the local investigator confirms all eligibility criteria apply.
- On study/enrolled: date eligibility is confirmed.
- On arm: date of enrollment.
- On treatment: first day treatment was given to the last day treatment was given.
- Off treatment: the last day treatment was given.
- On follow up: from last day of treatment to the end of follow-up period.
- Off study: follow-up period completed, with no additional data gathered.
- Withdrawn: subject fully withdraws consent (i.e., refuses ALL follow-up, even survival) or is taken off study by the local PI.

## **4.2 Prescreening and Screening Log**

The MCW study PI regularly reviews screen failure reasons to understand barriers to accrual and consider amending eligibility criteria. Screen failures are defined as participants who were considered for the trial to participate in the clinical trial with or without consent but are not subsequently assigned to the study intervention or enrolled in the study. MCWCC CTO will follow its SOPs regarding prescreening and screening tracking.

## **4.3 Consent**

Investigators or their appropriate designees will identify potentially eligible subjects from their clinics, subject self-referrals, referrals from other clinicians and/or other IRB-approved recruitment methods. No study conduct, including subject prescreening, can occur until after IRB approval.

A written, signed informed consent form (ICF) must be obtained before any study-specific assessments are initiated. A signed ICF copy will be given to the subject and a copy will be filed in the medical record (per local IRB policies and SOPs). The original will be kept on file with the study records.

After consent, an OnCore® new subject entry occurs must occur within 24 hours of consent.

## **4.4 Screening Procedures**

Refer to the study calendar of events.

Visit procedures that were performed as standard of care prior to consent (without the specific intent to make the subject eligible for the trial), may count toward screening tests and eligibility if they are within the screening window.

#### 4.5 Eligibility Criteria

Study staff must adhere to MCWCC CTO SOPs regarding eligibility review/confirmation.

No waivers of protocol eligibility will be granted, but when clinical factors relating to an eligibility item are unclear or questionable, the study PI ([name], [[contact]](mailto:[contact])) can only provide guidance or clarification on eligibility.

#### Inclusion Criteria

1. Clinical diagnosis of oral cavity squamous cell cancer.
2. Patient can start study agent administration but histological confirmation of squamous cell cancer (SCC) of the oral cavity (or histologic variants of SCC) by the pathologist must happen within seven days of registration in order to continue study agent administration.
3. Clinical stage II-IVA (as defined by the AJCC, 8th Edition) and amenable to surgical resection
4. New diagnosis of oral SCC, new second primary, or recurrent oral SCC following a minimum remission of six months following previous definite surgery.
5. History and physical examination by an otolaryngologist and medical oncologist within 14 calendar days of study registration.
6. Study agent administration should start within seven days of registration.
7. Patient must receive administration of study agent for a minimum of seven days.
8. ECOG Performance status  $\leq 2$ .
9. Age  $\geq 18$  years.
10. CBC/differential obtained within 14 calendar days prior to registration, with adequate bone marrow function defined as follows:  
Absolute neutrophil count (ANC)  $\geq 1,500$  cells/mm^3;  
Platelets  $\geq 100,000$  cells/mm^3;  
Hemoglobin  $\geq 8.0$  g/dl (Note: The use of transfusion or other intervention to achieve Hgb  $\geq 8.0$  g/dl is acceptable.);
11. Adequate renal and hepatic function within 14 calendar days prior to registration, defined as follows:  
Serum creatinine  $< 1.5$  mg/dl or creatinine clearance (CrCl)  $\geq 50$  ml/min within 14 calendar days prior to registration, determined by 24-hour collection or estimated by Cockcroft-Gault formula:  
CrCl male =  $[(140 - \text{age}) \times (\text{wt. in kg})] / [(\text{Serum Cr mg/dl}) \times (72)]$   
CrCl female =  $0.85 \times (\text{CrCl male})$

CRC Initials: \_\_\_\_\_

Date: \_\_\_\_\_

Investigator/Enrolling Physician Initials: \_\_\_\_\_

Date: \_\_\_\_\_

Subject Initials: \_\_\_\_\_ Subject Study ID: \_\_\_\_\_ Enrolling Physician \_\_\_\_\_

12. Total bilirubin < 2 x the institutional ULN within 14 calendar days prior to registration.
13. AST or ALT  $\leq$  3 x the institutional ULN within 14 calendar days prior to registration.
14. Magnesium, calcium, glucose, potassium, and sodium within 14 calendar days prior to registration, with the following required parameters:
  - Magnesium: > 0.9 mg/dl or < 3 mg/dl;
  - Calcium: > 7 mg/dl or < 12.5 mg/dl;
  - Glucose: > 40 mg/dl or < 250 mg/dl;
  - Potassium: > 3 mmol/L or < 6 mmol/L;
  - Sodium: > 130 mmol/L or < 155 mmol/L.
15. Female patients must meet one of the following:
  - Postmenopausal for at least one year before the screening visit, or
  - Surgically sterile (i.e., undergone a hysterectomy or bilateral oophorectomy), or
  - If subject is of childbearing potential (defined as not satisfying either of the above two criteria), agree to practice two acceptable methods of contraception (combination methods requires use of two of the following: diaphragm with spermicide, cervical cap with spermicide, contraceptive sponge, male or female condom, hormonal contraceptive) from the time of signing of the informed consent form through 90 days after the last dose of study agent, AND
    - Agree to practice true abstinence when this is in line with the preferred and usual lifestyle of the subject. (Periodic abstinence [e.g., calendar, ovulation, symptom-thermal, post ovulation methods] and withdrawal are not acceptable contraception methods.)
16. Male patients, even if surgically sterilized (i.e., status postvasectomy), must agree to one of the following:
  - Practice effective barrier contraception during the entire study period and through 60 calendar days after the last dose of study agent, OR
  - Must also adhere to the guidelines of any study-specific pregnancy prevention program, if applicable, OR
  - Agree to practice true abstinence when this is in line with the preferred and usual lifestyle of the subject. (Periodic abstinence [e.g., calendar, ovulation, symptom-thermal, post ovulation methods] and withdrawal are not acceptable methods of contraception.)
17. Patients must be deemed able to comply with the study plan.
18. Gastric tube study agent administration is permissible.
19. Patients must provide study-specific informed consent prior to study entry.

CRC Initials: \_\_\_\_\_

Date: \_\_\_\_\_

Investigator/Enrolling Physician Initials: \_\_\_\_\_

Date: \_\_\_\_\_

Subject Initials: \_\_\_\_\_ Subject Study ID: \_\_\_\_\_ Enrolling Physician \_\_\_\_\_

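### Inclusion criterion 14 joins its lower and upper laboratory limits with 'or', so as written no magnesium, calcium, glucose, potassium or sodium value can fail it

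*Combined protocol and SAP*

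**What the plan says.** Criterion 14 opens: "Magnesium, calcium, glucose, potassium, and sodium within 14 calendar days prior to registration, with the following required parameters". Five lines follow, one for each analyte, and every line gives a lower and an upper limit with 'or' between them. The potassium line, for example, is "Potassium: > 3 mmol/L or < 6 mmol/L". The other four are built in the same way. Their lower and upper limits are 0.9 and 3 mg/dl for magnesium, 7 and 12.5 mg/dl for calcium, 40 and 250 mg/dl for glucose, and 130 and 155 mmol/L for sodium.

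The introduction to section 4.5 rules out waivers. Where the clinical facts behind an item are in doubt, it says that the PI "can only provide guidance or clarification on eligibility". The section ends with a sign-off in which the coordinator and the enrolling physician confirm that every criterion was reviewed and the subject is eligible.

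**The concern.** The lead-in calls the figures required, so each line should define a range that a result must lie inside. Joined by 'or', the two limits become alternatives, and meeting either one is enough. Because the lower limit is smaller than the upper in every line, any value meets at least one of them.

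What is at stake is eligibility and its audit trail. Under section 4.1 a subject becomes eligible when the investigator confirms that all criteria apply, and section 4.5 is the signed record of that. On the literal reading, enrolling a patient outside a printed limit does not breach the line, and a screen failure for the same value rests on inferred intent. Two members of staff could treat one result in opposite ways, and each could defend the decision. Section 8.3 classes the protocol as high risk and subject to internal quality assurance review, and section 4.2 has the PI review screen-failure reasons. Both need a criterion with one meaning.

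**Working it through.** **Inputs.** The five pairs of limits are those printed in criterion 14. Write L for the lower limit, U for the upper limit and x for the result.

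**Rule as written.** A result passes if x > L or x < U. It fails only if x ≤ L and x ≥ U together. With L < U this is impossible, so the set of failing values is empty. Equivalently, the two accepted half-lines overlap by U − L, and a positive overlap means that together they cover every value.

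**Rule with 'and'.** A result passes if x > L and x < U, so it fails if x ≤ L or x ≥ U.

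| Analyte | L | U | Overlap U − L | Rejected as written | Rejected with 'and' |
|---|---|---|---|---|---|
| Magnesium (mg/dl) | 0.9 | 3 | 3 − 0.9 = 2.1 | none | ≤ 0.9 or ≥ 3 |
| Calcium (mg/dl) | 7 | 12.5 | 12.5 − 7 = 5.5 | none | ≤ 7 or ≥ 12.5 |
| Glucose (mg/dl) | 40 | 250 | 250 − 40 = 210 | none | ≤ 40 or ≥ 250 |
| Potassium (mmol/L) | 3 | 6 | 6 − 3 = 3 | none | ≤ 3 or ≥ 6 |
| Sodium (mmol/L) | 130 | 155 | 155 − 130 = 25 | none | ≤ 130 or ≥ 155 |

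All five overlaps are positive. As written, 0 of 10 limits exclude a value; with 'and', all 10 do. Evaluating both rules on a fine grid from 0 to 4U for each analyte, including the limits themselves, gave the same result: no rejections under 'or', and rejections at and beyond both limits under 'and'.

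**Spot checks for potassium as written.** 2 passes because 2 < 6. 8 passes because 8 > 3. A value of exactly 3 passes because 3 < 6.

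**Does the checklist use 'or' loosely?** No. Criterion 11 uses it for a true alternative: a serum creatinine limit or a creatinine clearance limit. Criteria 15 and 16 use it between options of which one suffices, and criterion 15 prints 'AND' where a further condition is added. A literal reader therefore has grounds within the document to read criterion 14 as alternatives.

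**Does another section supply the range?** No.

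- Study Calendar footnote 6 lists the five analytes in the metabolic panel without limits.
- The Protocol Summary asks for normal organ function without numbers.
- Exclusion criterion 7 covers severe active comorbidity and sets no laboratory limit.

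**The case against.** The strongest reply is that nobody will be misled. The lead-in makes the intent plain, and a coordinator or physician is unlikely to read the potassium line as accepting 2 or 8. A screen failure could cite the lead-in and the printed figures. Section 4.5 lets the PI clarify doubtful items and sends staff to institutional SOPs on eligibility review, which are not reproduced. There are further safeguards: criterion 5 requires history and examination by an otolaryngologist and a medical oncologist, section 5.7 describes a mid-course metabolic panel, and section 4.6 provides for investigator-initiated withdrawal. The study is single-site with eight patients, and no analysis depends on this line. It can also be said that 'and' excludes values exactly at a limit, which the sponsor may not have meant.

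Most of this stands as a limit on the practical risk, but none of it repairs the text. The PI provision concerns unclear clinical factors, whereas here the laboratory value is clear and the rule is faulty. Section 9.5.3 requires protocol changes to be made by amendment, so an informal reading of 'or' as 'and' is a poor substitute. The later safeguards act after enrolment, or do not set limits for these analytes. On boundary values, the printed inequalities are already strict. Changing the connector leaves them as they are, and the sponsor can confirm them in the same amendment.

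**Conclusion.** The concern holds. As written, criterion 14 rejects no laboratory value for any of the five analytes: 0 of its 10 limits take effect, and only a missing result or one outside the 14-day window can fail it. This rests on the printed text and on L < U in each line; no numerical assumption is needed. That ranges were intended is an inference from the lead-in, though a strong one.

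The effect on enrolment cannot be computed, because the documents do not say how many candidates would fall outside a limit. The PK endpoint and the confidence-interval margin in section 7.1 do not depend on this criterion. It is a wording error that should be corrected because it disables a stated eligibility screen. No view is taken on whether the limits themselves are suitable.

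**What to change.** In all five lines replace 'or' with 'and', and leave the sponsor's figures and the 14-day requirement unchanged:

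- magnesium > 0.9 and < 3 mg/dl
- calcium > 7 and < 12.5 mg/dl
- glucose > 40 and < 250 mg/dl
- potassium > 3 and < 6 mmol/L
- sodium > 130 and < 155 mmol/L

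The cost is five one-word edits in an amendment, which sections 9.3 and 9.5.3 require to be signed by the investigator and approved by the IRB before use. No test is added, since all five analytes are already in the screening metabolic panel. The one trade-off is that a candidate outside a printed limit becomes clearly ineligible. If patients have already been enrolled, their screening results should be checked against the limits: at most 8 patients x 5 analytes = 40 values.
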